1.9. MAIN AND SECONDARY VARIABLES

As MAIN VARIABLE, endocannabinoids in saliva and plasma (2-AG, AEA, PEA, OEA, DHEA, 2-LG, 2-OG; pmol/ml) will be studied .

And as SECONDARY VARIABLES are going to be studied:

- The bacteriological profile of the oral cavity (the following bacterial strains: *Aggregatibacter actinomycetemcomitans* , *Porphyromonas gingivalis* , *Tannerella forsythia* , *Treponema denticola* , *Prevotella intermedia* , *Fusobacterium nucleatum* , *Parvimonas micra* , *Campylobacter rectus* , *Eikenella corrodens* , *Veillonella kindergarden* and *Actinomyces naeslundii* for periodontal disease; and *streptococci mutans* , *S. sanguis* , *S. mitior* , *S. salivarius* and *S. milleri* for dental caries) ,
- The concentration of inflammatory cytokines in saliva and blood (interleukin [IL]-1 β , IL-6, IL-8, IL-10, IL-17, leptin, adiponectin, vascular endothelial growth factor [VEGF], Interferon [IFN]- γ and Tumor Necrosis Factor [TNF]- α),
- Glucose management (fasting blood glucose (mg/ dL), insulin (mUI/mL), HbA1c (%), HOMA-IR, HOMA2-IR, QUICKY, HOMA2%S, HOMA2%B) ,
- Adiposity and atherogenic profile [BMI (kg/m²)], waist circumference (cm), waist/hip ratio, waist/height ratio, blood pressure (mmHg), triglycerides (mg/dL),

- total cholesterol (mg/dL), HDL cholesterol (mg/dL), LDL cholesterol (mg/dL), total cholesterol/HDL, LDL/HDL and Triglycerides/HDL ratios ,
- Salivary parameters through sialometry (salivary flow), salivary viscosity, salivary pH and the impact profile on oral health (OHIP-14sp; WHO questionnaire) .

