3.3. HYPOTHESIS

For all of the above, our **hypothesis** is the following: **the endocannabinoidome has a similar role in the oral microbiota as in the intestinal one, so that its deregulation produces dysbiosis and an inflammatory state in the oral cavity, which may be linked to the OCD appearance.**

In fact, elevated levels of the cannabinoids AEA and 2-AG have been found in the saliva of obese people²⁴. Furthermore, ECS has been described in the oral cavity²⁵⁻²⁷ and several studies have demonstrated the presence and physiological relevance of the endocannabinoidome in the salivary glands^{25,28}.

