3.4. AIMS

Based on this hypothesis, we propose the following main objective: **to study the possible differences in the levels of cannabinoids (2-AG, AEA, PEA, OEA, DHEA, 2-LG, 2-OG; pmol/ml), both in saliva and plasma, in a sample of patients with/without oral cavity disease, and with obesity and prediabetes, or with obesity and T2D.**

As secondary objectives will be studied:

- The bacteriological profile of the oral cavity (increase in the bacterial 16S rRNA amplicon, compared to the reference genes, for the following bacterial strains: *Aggregatibacter actinomycetemcomitans*, *Porphyromonas gingivalis*, *Tannerella forsythia*, *Treponema denticola*, *Prevotella intermedia*, *Fusobacterium nucleatum*, *Parvimonas micra*, *Campylobacter rectus*, *Eikenella corrodens*, *Veillonella kindergarten* and *Actinomyces naeslundii* for periodontal disease; and *streptococci mutans*, *S. sanguis*, *S. mitior*, *S. salivarius* and *S. milleri* for dental caries).

- Inflammatory cytokines in saliva and plasma (interleukin [IL]-1 β , IL-6, IL-8, IL-10, IL-17, leptin, adiponectin, vascular endothelial growth factor [VEGF], Interferon [IFN]- γ and Tumor Necrosis Factor [TNF]- α).

- Glucose management through fasting blood glucose levels (mg/dL), insulin (mUI/mL), HbA1c (%), HOMA-IR, HOMA2-IR, QUICKY, HOMA2%S, HOMA2%B.

- Adiposity and atherogenic profile, through BMI (kg/m²), waist circumference (cm), waist/hip ratio, waist/height ratio, blood pressure (mmHg), triglycerides (mg/dL), total cholesterol (mg/dL), HDL cholesterol (mg/dL), LDL cholesterol (mg/dL), total cholesterol/HDL, LDL/HDL, and Triglycerides/HDL ratios.

- Salivary parameters (sialometry (salivary flow), salivary viscosity, salivary pH and the impact profile on oral health (OHIP-14sp; WHO questionnaire)).

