5.2. SAMPLE SIZE

Based on previous publications that have reported the levels of endocannabinoids in saliva (20), at least 12 subjects are needed to detect as significant differences of 0.5pmol/ml of AEA and 25pmol/ml of 2-AG, which are the differences found between healthy people and obese people. It is intended to recruit 15 people with obesity, prediabetes and a healthy mouth, 15 people with obesity, prediabetes and a diseased mouth, 15 people with obesity, diabetes and a healthy mouth, and 15 people with obesity, diabetes and diseased mouth. To differentiate a healthy mouth from a diseased mouth, a complete oral evaluation will be carried out on all participants, which includes a review of the mucous membranes, an evaluation of the bacterial plaque and the presence of dental caries, and an evaluation of the health of the teeth, gums, including the depth of probing and the presence of gingival bleeding (see point 5.6).

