7.2. STATISTICAL ANALYSIS

For the statistical study, the statistical software package SPSS 25.0 will be used. A database equivalent to the data collection notebook will be created with all the variables. First, the sample will be studied (descriptive statistics) using absolute and relative frequencies and then inferential statistics will be performed. The parametricity of the variables will be studied using a normality test. The parametric analysis will be carried out using ANOVA, followed by the corresponding post-test analysis. If the distribution of the variable is not normal, it will be converted to log or a non-parametric test will be used to contrast the differences. All hypothesis contrasts will be made with a significance level of 5%.

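### Fourteen unranked main endocannabinoid outcomes are each tested at 5% with no control across outcomes, so the chance of a false-positive main result exceeds 5%

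*Protocol*

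**What the plan says.** - **Main outcomes.** Protocol section 1.9: "As MAIN VARIABLE, endocannabinoids in saliva and plasma (2-AG, AEA, PEA, OEA, DHEA, 2-LG, 2-OG; pmol/ml) will be studied". Section 3.4 repeats the list as the main objective: "to study the possible differences in the levels of cannabinoids (2-AG, AEA, PEA, OEA, DHEA, 2-LG, 2-OG; pmol/ml), both in saliva and plasma". Neither section names a lead lipid or a lead fluid.
- **Test.** Section 7.2: "The parametric analysis will be carried out using ANOVA, followed by the corresponding post-test analysis". Variables that are not normal are log-transformed or tested non-parametrically. The post-test is not named.
- **Level.** Section 7.2 ends: "All hypothesis contrasts will be made with a significance level of 5" per cent. No section states an adjustment across outcomes or an exploratory reading of the p-values.
- **Sample size.** Section 5.2 argues from salivary data ("Based on previous publications that have reported the levels of endocannabinoids in saliva") and from two lipids: "at least 12 subjects are needed to detect as significant differences of 0.5pmol/ml of AEA and 25pmol/ml of 2-AG". It does not call those two primary.
- **Purpose.** The study is labelled descriptive and observational (sections 1.7 and 4.1). Section 3.3 nevertheless states a hypothesis about the endocannabinoid system, that "its deregulation produces dysbiosis and an inflammatory state in the oral cavity, which may be linked to the OCD appearance". Section 7.2 adds that, after the descriptive step, "then inferential statistics will be performed".

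**The concern.** With 14 main outcomes, one 5% test for each and no order among them, any of the 14 can carry the main claim. A single nominally significant lipid in one fluid could then be presented as support for the OCD hypothesis, and a reader could not tell it from the chance finding that 14 tests at 5% often produce. The post-test does not help: it limits false positives among the four groups for one lipid and does nothing across lipids or fluids.

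**Working it through.** **Inputs from the protocol.** Seven lipids × two fluids = 14 outcomes (1.9, 3.4). Four groups of 15, 60 in all (1.10, 5.2). 5% per contrast (7.2). The 5% is a stated input, so there is no figure of the plan to reproduce on this point.

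**Assumptions.** Normal outcomes with a common correlation; Tukey as the post-test. The protocol gives no correlation and names no post-test, so a range is shown.

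**Step 1: omnibus ANOVA, no lipid differs.** If the outcomes are independent, P(at least one of 14 significant) = 1 − 0.95^14 = 0.512. With correlation, from simulation (20,000 runs per value, F test on 3 and 56 degrees of freedom):

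| Common correlation | 0 | 0.3 | 0.5 | 0.7 | 0.9 | 0.95 |
|---|---|---|---|---|---|---|
| At least one significant ANOVA | 51% | 45% | 36–37% | 27% | 15% | 11–12% |
| At least one OCD difference within a glycaemic group, after ANOVA and Tukey | 22–23% | 20% | 16% | 12% | 6–7% | about 5% |

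If lipids correlate within a fluid but not between saliva and plasma, the figures at 0.5, 0.7, 0.9 and 0.95 are 42%, 34%, 23% and 18% (ANOVA) and 19%, 15%, 9% and 7% (OCD difference).

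**Step 2: does adjusting the omnibus test cure it?** Suppose that OCD has no effect but the prediabetes and diabetes groups differ by 0.8 SD in all 14 lipids (an assumed size). The omnibus test is then mostly passed for a reason unrelated to OCD. Chance of at least one false OCD difference:

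| Common correlation | 0 | 0.5 | 0.7 | 0.9 |
|---|---|---|---|---|
| Current rule | 26% | 18% | 13% | 7% |
| Benjamini-Hochberg on the 14 ANOVAs, then Tukey | 25% | 17% | 12–13% | 6–7% |

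Adjusting only the omnibus step therefore leaves the OCD error almost unchanged.

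**Step 3: adjust the OCD contrast itself.** Take one with- versus without-OCD contrast per outcome and apply Benjamini-Hochberg to the 14 p-values. The chance of any false OCD flag is 2% to 5%, both when nothing differs and when only glycaemic status matters.

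**Step 4: cost in power.** This was worked out for the four-group ANOVA, at the effect that has 80% power at 5% (f = 0.44). Under Benjamini-Hochberg across 14, the power per lipid is about 43% if one lipid truly differs, 63% to 65% if seven do, and 73% to 76% if all do. The smallest p-value faces 0.05/14 = 0.0036, which explains the first figure.

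**The case against.** **An analysis plan may deal with this.** Only the protocol is at hand, and multiplicity rules are often left to the analysis plan. The sentence in 7.2 sets a level, and an adjusted p-value is also compared with 5%. This stands in part: the per-contrast reading is the natural one but is still a reading. It does not remove the point, because the protocol fixes one level for every contrast and leaves 14 outcomes with equal standing.

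**The study is descriptive.** No treatment decision rests on one lipid, and section 3.2 says that no earlier study has examined these relationships. That limits the severity. It does not settle the matter, because the same protocol states a hypothesis, sizes the study on detecting significant differences and plans inferential tests.

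**The 51% overstates the harm.** This is fair. A reader might infer that the main result has an even chance of being false. The documents do not support that: 51% assumes independent lipids and counts any group difference, including one between prediabetes and diabetes alone. For the OCD difference the range is about 22% to 5%, and near a correlation of 0.95 across all 14 outcomes the excess disappears.

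**Salivary AEA and 2-AG are the real primaries.** A reader might infer this from section 5.2, but no section ranks them, and 1.9 and 3.4 place all 14 on the same footing.

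**Conclusion.** The point holds. Under the rule as written, the chance of at least one false significant ANOVA among the main outcomes is above 5% at every correlation tried: about 51% at 0, 36% at 0.5 and 12% at 0.95. For a false OCD difference it is about 22%, falling to about 5%. The direction follows from the text; the size rests on assumed correlations, normal outcomes and Tukey as the post-test. The data remain usable and the remedy is wording, so this should be fixed before results are seen but does not undermine the study. It would go too far to say that a significant lipid would be false, or that no adjustment can be planned elsewhere.

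**What to change.** Amend section 7.2 before results are seen:

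- Keep the 14 endocannabinoid outcomes as the main variable. For each, test one with- versus without-OCD contrast, and apply Benjamini-Hochberg at a 5% false discovery rate to those 14 contrast p-values, not only to the omnibus ANOVA. If the contrast is tested separately in prediabetes and in diabetes, the family is 2 × 14 = 28 p-values.
- Report all 14 outcomes with adjusted and unadjusted p-values.
- Label unadjusted p-values for the secondary variables as exploratory.

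**Alternative.** If salivary AEA and 2-AG are made primary, sections 1.9 and 3.4 must be changed to match, and the adjustment must again be on the OCD contrast.

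**Minimum, if no adjustment is wanted.** State that the 14 p-values are unadjusted and exploratory, report all 14, and do not claim that one significant lipid confirms the hypothesis.

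**Cost.** Wording, plus some power per lipid under adjustment. In the four-group ANOVA it falls from 80% to about 43% if only one lipid differs and to about 73% to 76% if all do. Those figures are for the omnibus test; power for the OCD contrast should be worked out once that contrast is fixed. The minimum option costs no power.

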8. ADVERSE EVENTS

Given the nature of this trial, no type of adverse event or adverse reaction is anticipated.

